5.3.2. Main Estimand of The Key Secondary Endpoint

Study Objective: To evaluate the efficacy of the study intervention 24 weeks off-treatment.

Scientific Question: in the adult population with chronic HBV infection

- a) what is the benefit of any of the JNJ-3989 doses (40mg, 100mg or 200 mg) (Arms 2-4) administered in combination with NA for 48 weeks in terms of functional cure 24 weeks after stopping all study interventions compared with historical control (5%)?
- b) what is the benefit of JNJ-3989 100 mg+JNJ-6379+NA (Arm 1) and JNJ-379+NA (Arm 5) for 48 weeks in terms of functional cure 24 weeks after stopping all study interventions compared with Historical Control (5%)?
- c) what is the benefit of JNJ-3989 100mg+NA with or without JNJ-6379 (Arm 1, 3) or JNJ-6379+NA (Arm 5) administered for 48 weeks in terms of functional cure 24 weeks after stopping all study interventions?

A) Study Intervention:

- Arm 1: JNJ-3989 (100 mg) + JNJ-6379 (250 mg qd) + NA

- Arm 2: JNJ-3989 (200 mg) + Placebo + NA
- Arm 3: JNJ-3989 (100 mg) + Placebo + NA
- Arm 4: JNJ-3989 (40 mg) + Placebo + NA
- Arm 5: Placebo + JNJ-6379 (250 mg qd) + NA
- Historical Control value of 5%

B) Study Population: HBeAg-positive and -negative chronic HBV-infected patients who are not being treated for their HBV infection (including treatment-naïve patients) or are virologically suppressed by being treated with NA.

C) Variable: Response status defined as participants who meet the criteria defining functional cure at Week 72 (responders) as in Section [5.3.1](#)

D) Intercurrent events:

- Treatment discontinuation prior to Week 48: if the participant discontinued treatment prior to Week 48 then s/he will be considered non-responder (composite strategy).
- Major protocol deviations affecting efficacy: [ATTACHMENT 1](#) identifies the deviations considered intercurrent event (in per protocol set 2 column [PP2]). Participants with such deviations and who have missing data for the endpoint will be considered as non-responders (composite strategy). For all other deviations not considered intercurrent events, the data are used regardless of the occurrence of major protocol deviations (treatment policy strategy).
- Deaths prior to Week 72 are handled in a composite strategy as participants who die prior to Week 72 will be considered as non-responders.
- NA re-treatment between Week 48 and 72: the participant will be counted as non-responder (composite strategy).

E) Population-level summary: Difference in proportion of participants with functional cure status at Week 72 between study intervention arms.

5.3.2.1. Main Estimator

5.3.2.1.1. Analysis Methods

5.3.2.1.1.1. Scientific Question Part a: JNJ-3989 Dose Response Trend Test and Dose Response Model Estimation

For the comparisons against NA control, the same multi-step testing strategy as the one implemented for the primary efficacy endpoint (see Sections [5.1.1](#) and [5.2.2.1.1](#)), using MCP-Mod and additional intervention arms pairwise comparisons against NA control in a fixed sequence, will be used to control the type 1 error for multiple testing. However, the comparisons with NA control in the testing strategy applied to this efficacy endpoint will be made against the NA historical control benchmark of 5%, instead of the study NA control arm (Arm 6).

The choice of 5% as the historical NA control percentage for the HBsAg seroclearance 24 weeks after 48-week NA treatment was based on the results of a meta-analysis (Slaets L. et al., 2020) of historical data available for more than 15 years of NA treatment in 3 different subgroups based on treatment history and HBeAg status. The upper limit of the 95% prediction interval of the percentage of seroclearance at the end of 48-week NA treatment, based on the meta-analytical predictive probability distribution, was the largest (4.17%) in the subgroup of treatment-naïve HBeAg-positive patients (see Table 8 in the Protocol Amendment 1). As the current study enrolls participants in all subgroups of treatment history and HBeAg status, the value of 5% is considered a conservative estimate. Given that the percentage of HBsAg seroclearance at the end of 48 weeks of NA treatment is not expected to differ substantially from that percentage 24 weeks later, the 5% value derived from this meta-analysis provides an adequate historical control point estimate of the functional cure endpoint.

The MCP-Mod analysis will use 5% as the point estimate for the functional cure rate of the historical control group. In simulations on the logit scale under the assumption that the null hypothesis is globally true, a variance of 0.0275 (on the logit scale) afforded a match between the observed and nominal Type-I error rate. For this value the simulated Type 1 error rate was 0.043 (upper 99% CI: 0.044). Further details are described in a separate document, the Modeling and Simulation Report (MSR) for this study.

Therefore, within the MCP-Mod framework, the MCP analysis to test the null hypothesis that none of the 3 JNJ-3989 doses (40 mg, 100 mg, and 200 mg)+NA is better than historical control NA (i.e. the flat dose response curve) will assume:

- the point estimate for the response rate of the “JNJ-3989 dose=0 mg historical NA” is 0.05,
- the estimated variance, on the logit scale, of the point estimate for the response rate of the “JNJ-3989 dose=0 mg historical NA” historical group is 0.0275.

Characterization of the dose-response model: The model averaging techniques (Bornkamp B. et al., 2009) across the candidate models will be utilized to derive the dose-response shape and to evaluate the desired dose(s) of JNJ-3989 (modeling step). The estimated dose response curve and the corresponding confidence band will be plotted against the JNJ-3989 dose range of 0 mg to 200 mg.

5.3.2.1.1.2. Scientific Question Part b: Pairwise Comparisons vs Historical Control

For the pairwise comparison against the fixed historical control value of 5% for Arms 1 and Arm 5, respectively, the Clopper-Pearson test will be used at one-sided 0.05 alpha level, based on a fixed sequence testing approach as described in Section 5.1.1.

5.3.2.1.1.3. Scientific Question Part c: Comparisons Among Combination Regimens

For the regimen-finding objective, the testing among the regimens (Arm 1, 3, and 5) will be performed at a one-sided 0.025 alpha level using the min test approach to provide evidence of superior efficacy of the triple regimen Arm 1 over the dual regimens Arm 3 and Arm 5, for

regulatory consideration. This analysis is performed at a more stringent α -level because it aims to support the selection of the combination drug therapy to be studied in confirmatory studies. The JNJ-3989+JNJ-6379+NA combination regimen Arm 1 will be declared statistically superior to the dual regimens Arm 3 and Arm 5, if both tests of Arm 1 vs Arm 3 and Arm 1 vs Arm 5 demonstrate statistical significance at the one-sided 0.025 level. The Mantel-Haenszel test for the difference of 2 proportions adjusted for the 2 randomization stratification factors will be applied.

Further, the functional cure efficacy endpoint will be summarized for the control Arm 6 with the point estimate paired with its 90% CI using the Clopper-Pearson exact method to assess the consistency with the assumed historical control value of 5%.

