5.1.1. Level of Significance

The study addresses two separate research questions:

- 1) Dose finding: the comparisons of 3 doses of JNJ-3989+NA (Arms 2, 3, and 4) against NA treatment alone (Arm 6) and other comparisons of active regimens (Arm 1 and Arm 5) vs Arm 6,
- 2) Regimen finding: the comparisons of the combination regimen of JNJ-3989 (100 mg) +JNJ-6379 +NA (Arm 1) vs each of the mono components JNJ-3989 (100 mg) and JNJ-6379, respectively, on the background of NA (Arm 3 and Arm 5).

For the primary efficacy endpoint analysis, the Type 1 error rate is controlled at 0.05 one-sided level for multiple comparisons within each separate research question differently and independently.

For the comparisons against the control, a fixed sequence approach is used where the first step implements the multiple contrast test of the MCP-Mod methodology (applied to Arms 2, 3, 4, and 6) to detect a trend test among the JNJ-3989 doses (40 mg, 100 mg and 200 mg), under the null hypothesis of no differences across the four arms, which is followed by the pairwise comparison of Arm 1 vs Arm 6, followed by the pairwise comparison of Arm 5 vs Arm 6. Based on the fixed sequence principle, each step must be found statistically significant at a one-sided 0.05 level in order to proceed to the next step.

For the comparisons among the regimens (Arms 1, 3, and 5), the min test principle is used. The JNJ-3989+JNJ-6379+NA combination regimen Arm 1 will be declared statistically superior to the dual regimens (Arm 3 and Arm 5) if both tests of Arm 1 vs Arm 3 and Arm 1 vs Arm 5 demonstrate statistical significance at the one-sided 0.05 level.

For the key secondary endpoint, the same multi-step testing strategy as the one implemented for the primary efficacy endpoint described above, using MCP-Mod and additional treatment arms pairwise comparisons against control in a fixed sequence, as well as the min test approach separately for between-regimen comparisons, will be used for this key secondary endpoint. However, the comparisons with NA control in the testing strategy applied to this efficacy endpoint will be made against the NA historical control benchmark of 5%, instead of the study NA control arm (Arm 6).

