5.2.2.1. Main Estimator

5.2.2.1.1. Analysis Methods

5.2.2.1.1.1. Scientific Question Part a: JNJ-3989 Dose Response Trend Test and Dose Response Model Estimation

[figure not shown]
Statistical Model: For the JNJ-3989 dose-finding objective, a hybrid methodology that combines aspects of multiple testing with modeling techniques (MCP-Mod) will be used for evaluating a dose-response trend and estimating the dose-response relationship of 3 JNJ-3989 doses in combination with NA (Arm 2, 3 and 4) versus NA treatment alone (control Arm 6). Because the primary efficacy endpoint is binary, the generalized MCP-Mod approach ([Pinheiro J. et al, 2014](#)) will be used on the logit scale. Following the notation in Pinheiro et al (2014), the “dose-response parameter” estimates and their variance-covariance matrix will be obtained from a logistic regression with JNJ-3989 dose treated as a factor, where Arm 6 corresponds to “JNJ-3989 dose=0

mg”. The Firth's penalized likelihood method (Firth D., 1993 & Heinze G. et al., 2002) will be used in the logistic regression to reduce possible bias which could arise in the presence of a zero response rate at one or more dose levels

If one or more prespecified models are found to be significant (multiple contrast test approach), a significant trend test among Arms 2, 3, 4, and 6 (JNJ-3989 40 mg, 100 mg and 200 mg and NA control), under the null hypothesis of no differences across the 4 arms will be declared.

A set of 5 candidate models (see [Figure 1](#)) was prespecified as possible dose-response shapes in terms of the logit of the primary efficacy endpoint. The 5 candidate models are the EMax1 (ED₅₀=5 mg), EMax2 (ED₅₀=100 mg), Linear, Exponential (d=40) and Sigmoid Emax model (ED₅₀=110 mg, h=8). A dose-response trend is established when the maximum of the t-test statistics exceeds the critical value at the one-sided 0.05 alpha.

Figure 1: Candidate Dose-response Models on the Logit Scale

Characterization of the dose-response model: The model averaging techniques (Bornkamp B. et al., 2009) across the candidate models will be utilized to derive the dose-response shape and to evaluate the desired dose(s) of JNJ-3989 (modeling step). The estimated dose response curve and the corresponding 90% confidence band will be plotted against the JNJ-3989 dose range of 0 mg to 200 mg.

5.2.2.1.1.2. **Scientific Question Part b: Pairwise Comparisons vs Control Arm**

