5.3.2.1.2. Data Included

All available data from mITT analysis set, is included after taking into account all the intercurrent events and applying the intercurrent event strategies specified in Section 5.3.2.

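### Does the historical-control variance of 0.0275 hold the Type I error of the functional-cure trend test when the SAP does not state the contrast rule?

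*SAP*

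**What the plan says.** SAP 5.3.2.1.1.1 tests the three JNJ-3989 doses for functional cure using "the same multi-step testing strategy as the one implemented for the primary efficacy endpoint", with a fixed 5% historical rate in place of Arm 6. It cross-refers to SAP 5.2.2.1.1. There the dose "estimates and their variance-covariance matrix will be obtained from a logistic regression with JNJ-3989 dose treated as a factor", and Firth's penalised likelihood "will be used in the logistic regression to reduce possible bias which could arise in the presence of a zero response rate".

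Dose 0 enters with point estimate 0.05 and logit variance 0.0275. The variance was tuned: "In simulations on the logit scale under the assumption that the null hypothesis is globally true", 0.0275 brought the observed error into line with the nominal one. "For this value the simulated Type 1 error rate was 0.043 (upper 99% CI: 0.044"), the SAP adds, and it refers to the Modeling and Simulation Report for details. The purpose of the test is "to test the null hypothesis that none of the 3 JNJ-3989 doses" is better than the historical control.

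SAP 5.1.1 makes this test the first step of a fixed sequence: "each step must be found statistically significant at a one-sided 0.05 level in order to proceed to the next step". The arm sizes are those of the mITT set (SAP 5.3.2.1.2: "All available data from mITT analysis set, is included after taking into account all the intercurrent events").

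**The concern.** The variance 0.0275 is not an estimate from the meta-analysis. It is a constant chosen so that one particular test has about the right level. If the Week 72 analysis uses another estimator, or other contrast weights, than the simulation did, the level can move.

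Two facts make this more than a formality. First, the historical control is a fixed number and does not pass through the Firth fit, so the shift that Firth gives to the dose logits does not cancel against control. Second, neither SAP 5.2.2.1.1.1 nor Protocol 9.4.1.1 says whether the optimal contrasts are computed from a planned covariance or recomputed from the observed one.

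If the first step ran above 0.05, a false dose-response claim would be too likely, and the comparisons of Arm 1 and Arm 5 against 5% would open too often.

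**Working it through.** **Inputs.** Control rate 0.05, fixed, with logit variance 0.0275 (SAP 5.3.2.1.1.1). Three dose arms of 90 (SAP 1.4). Five candidate shapes: Emax with ED50 5 and 100, linear, exponential with delta 40, sigmoid Emax with ED50 110 and h 8 (SAP 5.2.2.1.1.1). One-sided 0.05. No missing data (assumption).

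**Formulas.** With x responders out of n:
- Firth logit = log((x+0.5)/(n−x+0.5)); variance = 1/(n p(1−p)), with p = (x+0.5)/(n+1).
- Unpenalised logit = log(x/(n−x)), with a small substitute when x = 0.
- Test statistic = maximum over the five shapes of c'm/√(c'Sc), where m holds the four logits and S the variances. It is compared with the 95% quantile of that maximum under the multivariate normal.
- Planned dose-arm variance at 5% = 1/(90 × 0.05 × 0.95) = 0.234.

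All outcomes of three binomial arms at a true 5% were enumerated.

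**Why the estimator matters.** At n=90 and x=4 the Firth logit is log(4.5/86.5) = −2.956, against −3.068 unpenalised. At x=5 it is log(5.5/85.5) = −2.744, against −2.833. The dose logits rise by about 0.1, while control stays at log(0.05/0.95) = −2.944.

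**The SAP's own figure.** Unpenalised logits with re-optimised contrasts give 0.043 to 0.044 at n=90. Firth with equal-weight contrasts gives 0.042 to 0.043 at n=95. The SAP's 0.043 is thus reachable in more than one way and does not show which set-up was used.

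**Firth with 0.0275, n=90, true rate 5%:**

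| Contrast rule | Type I error |
|---|---|
| Re-optimised on observed covariance | 0.063 |
| Fixed, planned covariance | 0.050 |
| Fixed, equal weights | 0.046 |
| Fixed, 45:90:90:90 weights | 0.039 |

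A t critical value with 267 degrees of freedom changes the first two only slightly, to 0.062–0.063 and 0.049.

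**Re-optimised rule by true rate in all three arms, n=90:**

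| True rate | Error |
|---|---|
| 5% | 0.063 |
| 4.83% | 0.050 |
| 4.5% | 0.031 |
| 4.17% | 0.018 |
| 3% | 0.002 |
| 1% | 0.000 |

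**Where the control rate is likely to lie.** Protocol Table 8 gives mean seroclearance of 0.67%, 0.19% and 0.15% in the three subgroups, with upper prediction limits of 4.17%, 3.33% and 1.06%. The planned mix is 40% not currently treated, of whom 40% are expected to be HBeAg-positive: 16%, 24% and 60%. With every subgroup at its upper limit, the mixture is 0.16 × 4.17 + 0.24 × 3.33 + 0.60 × 1.06 = 2.1%. At that rate the error is below 0.002 even under the adverse rule.

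**The case for a change.** The best case for a change is that the stated null has its boundary at 5%, so the level must hold there however unlikely that rate is. Taking both estimates and covariance from the Firth fit, and deriving the contrasts from that covariance, is a natural reading of SAP 5.2.2.1.1.1. Under it the error is 0.063, about a quarter above nominal (0.063/0.05 = 1.26), and it is 0.058 to 0.073 at every arm size from 76 to 100. Two statisticians working from the SAP alone could run different tests.

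The arithmetic stands, and so does the observation that the contrast rule is missing from the SAP text. The step to a defect does not. The regression covariance is needed to studentise fixed contrasts as much as to re-optimise them, so that passage does not choose between the rules. The simulation report may state both the rule and the estimator.

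Prescribing a rule now is not free of cost either:
- **Power.** Against the 0.063-level test at an assumed 10% top-dose cure rate, planned-covariance contrasts lose 1.8 to 4.6 points and equal weights 6.9 to 9.7. Part of that is the price of holding 0.05.
- **Level.** Planned-covariance contrasts with 0.0275 kept give about 0.051 at n=89 to 93. That is a plausible range, since about 5% over-enrolment (90 × 1.05 = 94.5 per arm) is followed by mITT exclusions.
- **Timing.** The sponsor is fully unblinded at the Week 48 analysis (SAP 1.5), and the history of SAP Amendment 2 refers to interim analyses already done. Re-tuning the constant at observed arm sizes would alter a prespecified quantity after unblinding.

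**Conclusion.** No change to the plan follows. The analysis estimator is given by cross-reference. What the SAP leaves out is the estimator behind the calibration and the contrast rule. It places the calibration details in the Modeling and Simulation Report, and the sensible way to fill the gap is to run the analysis under the rule used there.

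The possible excess is 0.063 against 0.05 at n=90. It needs Firth estimates, contrasts re-optimised on the observed covariance, and all three doses at almost exactly 5%. Contrasts fixed in advance hold 0.05 to rounding at n=90, and below a true rate of about 4.8% even the adverse rule is within its level.

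The consequences are also limited. This is a key secondary test supporting dose selection in Phase 2b. SAP 5.3.4 repeats the comparison against concurrent Arm 6 without the constant, and the 0.025-level regimen tests do not use it.

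The figures assume equal arms and no missing data. Pooling over imputations (SAP 5.3.2.1.4) would lower them. They also rest on not having seen the simulation report: if it showed a calibration under a different estimator or rule from the one applied, the quoted 0.043 would need restating.

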5.3.2.1.2. Data Included

All available data from mITT analysis set, is included after taking into account all the intercurrent events and applying the intercurrent event strategies specified in Section 5.3.2.

5.3.2.1.3. Assumptions

- Missing Data for HBsAg are Missing at Random (MAR)
- The treatment effect is homogeneous across randomization stratification strata

5.3.2.1.4. Missing Data Handling Rule

Participants who withdraw from the study prior to Week 72 will be considered as non-responders.

If a participant remains in the study after experiencing a major protocol deviation (defined for the purpose of efficacy analyses and is an intercurrent event) and has missing Week 72 value, then the imputation to non-response will be applied. If the value for the endpoint at Week 72 is available, then such data will be used to determine their response status.

For the participants still in the study at Week 72 or for participants that have neither discontinued treatment early nor experienced any major protocol violations (defined for the purpose of efficacy analyses and is an intercurrent event), and HBsAg values missing at Week 72, then the primary method to handle missing data will be the Multiple Imputation (MI) approach ([Ratitch B. et al., 2013](#)) under the assumption of MAR will be applied to a model for continuous HBsAg log values over time.

The MI model will use all available data and be applied to the continuous log-transformed HBsAg values (not the binary endpoint). Of note, also the pre-ICE data for those subjects who experienced an ICE will be included in the MI model; but for these subjects the response status will be applied according to the ICE strategies before running the MI model.

The model will include treatment, the 2 randomization factors and the available non-missing log-transformed HBsAg (values < LLOQ, TND or TD will be first substituted following rules described in [Table 3](#)) for each scheduled time point (Week) and the following demographic and baseline characteristics ([King G. et al., & Honaker J. et al.](#)): age, gender, and baseline log-transformed value for HBsAg level.

A total of 200 datasets will be generated where both intermittent and monotone missing HBsAg values will be imputed for each subject relying on non-missing data from all other subjects within the same treatment group. Once the 200 completed datasets are generated by filling in the missing data with samples from the imputation model, the key secondary endpoint response status (binary variable) will be derived using both imputed and observed HBsAg values at Week 72.

For the MCP-step, the max trend test will be obtained for each of the imputed datasets and the multiplicity adjusted p-value associated with the largest T-test statistic will be saved. All p-values will be transformed to a Z-test statistic using the inverse cumulative distribution function of the standard normal distribution. The resulting 200 Z-test statistics and their standard error of 1 will be combined into an overall Z test result, using SAS PROC MIANALYZE.

For Mod-step, model averaging techniques across all 5 candidate models will apply to each imputed dataset and produce the weighted estimates across all models of the treatment effect across the JNJ-3989 dose range (0 mg and 200 mg). The standard errors will be obtained using bootstrapping techniques and then combined into one result using PROC MIANALYZE. The final response estimates on the logit scale for each dose level in the range 0 mg to 200 mg and their 90% CI will be back transformed to the original scale of proportion of responders and plotted with the corresponding 90% confidence band.

For pairwise comparisons against the fixed historical control value of 5% for Arm 1 and Arm 5, the estimated proportion with the asymptotic standard error will be obtained for each dataset. Then the results from these multiple imputed datasets are combined (pooled) for obtaining the overall inference and p-value in a way that accounts for the variability between imputations ([Ratitch B. et al., 2013](#)). Depending on the amount of missing data, the number of imputed datasets to be generated will be increased appropriately to ensure robustness in the results ([Graham JW. et al., 2007](#)).

For comparisons amongst combination regimens (Arms 1, 3, and 5), the MH test will be performed for each dataset to generate individual estimates of the difference in proportions and the standard error adjusted on stratification factors. Then the results from these multiple imputed datasets are combined (pooled) for obtaining the overall inference and p-value in a way that accounts for the variability between imputations ([Ratitch B. et al., 2013](#)). Depending on the amount of missing data, the number of imputed datasets to be generated will be increased appropriately from the planned 200 to ensure robustness in the MI results.

